7.1.1 Procedures for discontinuation of study treatment

The investigator should instruct the subject to contact the site before or at the time if study treatment is stopped. A subject that decides to discontinue study treatment will always be asked about the reason(s) and the presence of any AEs. The date of last intake of study treatment should be documented in the eCRF. All study treatment should be returned by the subject at their next on-site study visit or unscheduled visit. Subjects permanently discontinuing study treatment should be given locally available standard of care therapy, at the discretion of the investigator.

Discontinuation of study treatment, for any reason, does not impact on the subject's participation in the study. The subject should continue attending subsequent study visits and data collection should continue according to the study protocol. Patients who have

permanently discontinued from further receipt of IP will need to be discontinued from the IRT/RTSM.

An EoT visit is required for safety assessments for any subjects who permanently discontinue study treatment for any reason (except for death, lost to follow-up, or withdrawal of consent), including disease progression. The end of treatment visit is not required for subjects who discontinue from study treatment within 10 days of a scheduled study visit or if the EoT visit would be performed within 14 days of the safety follow-up visit. If the SFU visit is within ± 7 days of a regularly scheduled visit during the post-treatment phase, the visits may be combined into a single visit.

In addition to the EoT visit, an SFU visit should be conducted at 30 (+7) days after his or her last dose of all study drugs to monitor for resolution or progression of AEs and to document the occurrence of any new events, regardless of whether the subject receives a new anticancer therapy or demonstrates disease progression within this time frame. Refer to Tables 1-3, for the assessments required for the EoT and SFU visits.

If the subject does not agree to continue in-person study visits, a modified follow-up must be arranged to ensure the collection of endpoints and safety information. This could be a telephone contact with the subject at end of treatment follow up visit, a contact with a relative or treating physician, or information from medical records. The approach taken should be recorded in the medical records. A subject that agrees to modified follow-up is not considered to have withdrawn consent or to have withdrawn from the study.

7.1.2 Follow-up for progression and survival

Post-treatment Disease Follow up: All subjects enrolled who complete the study treatment (Arm B) or discontinue from study treatment due to reasons other than disease progression will be followed for disease evaluation approximately every 12 weeks or 24 weeks from the latest date of disease evaluation before study treatment discontinuation until disease progression, regardless of whether the subject receives a new anti-CLL therapy.

Survival Follow up: All subjects who have disease progression and have not withdrawn consent will be contacted approximately every 24 weeks by clinical visit or telephone, to assess survival and the use of alternative anti-CLL therapy and occurrence of any secondary malignancies until death or lost to follow up. At the time of the planned final analysis, a survival sweep may be conducted. All subjects who are on study and not known to have died before the survival sweep may be contacted at that time.

7.2 Lost to follow-up

A subject will be considered potentially lost to follow-up if he or she fails to return for scheduled visits and is unable to be contacted by the study site.

The following actions must be taken if a subject fails to return to the clinic for a required study visit:

- The site must attempt to contact the subject and reschedule the missed visit as soon as possible and counsel the subject on the importance of maintaining the assigned visit schedule.
- Before a subject is deemed lost to follow-up, the investigator or designee must make every effort to regain contact with the subject or through their family, or by contact with subject's current physician, e.g., by repeat telephone calls, certified letter to the subject's last known mailing address, or local equivalent methods. If a public death registry is available, death information (i.e., date of death) should be collected where allowed by regulatory and EC requirements.
- All attempts to contact the subject should be made routinely and recorded in eCRF on the survival status module. The site should report the attempted date of contact and the last date known to be alive.
- If contact or registry/public source is unsuccessful (or no clear status can be obtained), list subject's status as "unknown" and continue the contact attempts until end of the study (until final analysis).
- Patients should not be marked as lost to follow-up on the Termination (DS) module until the end of the study (at final analysis) when all attempts to collect survival follow-up have been exhausted.
- At the time of final analyses, all enrolled subjects' survival status in the safety analysis set should be re-checked, including those subjects who have withdrawn consent or are classified as "lost to follow-up."
 - Subjects who have withdrawn consent: In the event that the subject has actively withdrawn consent to the processing of their personal data, the survival status of the subject can be obtained by site personnel from publicly available death registries (if available) where it is possible to do so under applicable local laws, to obtain a current survival status in the 7 days following data cut-off. (The applicable CRF modules will be updated.)
 - Subjects classified as lost to follow-up: Site personnel should check hospital records, the subject's current physician, and a publicly available death registry (if available) to obtain a current survival status in the 7 days following data cut-off. (The SURVIVE module will be updated.)

7.3 Withdrawal from the study

A subject may withdraw from the study (e.g., withdraw consent), at any time (investigational product and assessments) at his/her own request, without prejudice to further treatment.

If the subject withdraws consent for disclosure of future information, the sponsor may retain and continue to use any data collected before such a withdrawal of consent.

If a subject withdraws from the study, he/she may request destruction of any samples taken, and the investigator must document this in the site study records. If samples already have been analyzed at the time of the request, the sponsor will not be obliged to destroy the results of this research.

Such subjects will always be asked about the reason(s) and the presence of any AEs. The investigator will follow up subjects as medically indicated. The subject will return electronic ePRO device(s).

The sponsor or its delegate will request investigators to collect information on subjects' vital status (dead or alive; date of death when applicable) at the data cut-off for study analyses from publicly available sources, in accordance with local regulations. Knowledge of the vital status at data cut-off for study analyses in all subjects is crucial for the integrity of the study.

See the SoAs (Table 1, Table 2, and Table 3) for data to be collected at the time of study discontinuation and follow-up and for any further evaluations that need to be completed. Any remaining study treatment(s) should be returned by all subjects.

8 Study Assessments AND PROCEDURES

Study procedures and their timing are summarised in the SoA (Section 1.1). Descriptions of the scheduled evaluations are outlined in the subsections below. Before study entry, throughout the study, and at the follow-up evaluation, various clinical and diagnostic laboratory evaluations are outlined. The purpose of obtaining these detailed measurements is to ensure adequate safety and efficacy assessments. Clinical evaluations and laboratory studies may be repeated more frequently if clinically indicated. Such unscheduled assessments will be captured in the protocol-specific database as appropriate.

The investigator will ensure that data are recorded on the eCRFs. A web-based data capture (WBDC) system will be used for data collection and query handling.

The investigator ensures the accuracy and completeness of eCRFs and timeliness of the data recorded, and of the provision of answers to data queries according to the Clinical Study Agreement. The investigator will electronically sign the completed eCRFs. A copy of the completed eCRFs will be archived at the study site.

Immediate safety concerns should be discussed with the sponsor immediately upon occurrence or awareness to determine if the subject should continue or discontinue study treatment.

Adherence to the study design requirements, including those specified in the SoA, is essential and required for study conduct.

All screening evaluations must be completed and reviewed to confirm that potential subjects meet all eligibility criteria. The investigator will maintain a screening log to record details of all subjects screened and to confirm eligibility or record reasons for screening failure, as applicable.

Medical history must be collected and recorded including concurrent medical signs and symptoms, alcohol use and, if a smoker, cigarette use. Disease history, including the date of initial diagnosis, Rai staging within 28 days of first dose with study drug, and history of autoimmune CLL complications and their treatment will also be recorded based upon available documents and subject history.

Procedures conducted as part of the subject's routine clinical management (e.g., blood count) and obtained before signing of the ICF may be utilised for screening or baseline purposes, provided the procedures met the protocol-specified criteria and were performed within the timeframe defined in the SoA.

Repeat or unscheduled samples may be taken for safety reasons or for technical issues with the samples.

8.1 Efficacy assessments

8.1.1 Tumor assessments

Overall response assessments will be based upon evaluation of physical exams, recording of symptoms, radiologic evaluations, hematologic evaluations, and bone marrow exams per the SoA.

Baseline:

For baseline, a CT scan with contrast (or MRI if CT is contraindicated) is required within 28 days before the first dose of study drug and must include the neck, chest, abdomen, and pelvis and any other disease sites (e.g., brain). Spleen and liver size should be recorded in CT measurement. Additionally, bone marrow aspiration and biopsy are required within 60 days before first dose of study drug. Physical exam (especially lymph node and organomegaly), B-symptoms, blood counts with differential, and other clinical information at baseline should be recorded in the eCRF.

Up to 6 measurable disease sites (only nodal lesions ≥ 1.5 cm in the longest diameter, clearly measurable in 2 perpendicular dimensions), will be followed as target lesions for each subject. Measurable sites of disease should be chosen such that they are representative of the subject's disease. In addition, selection of target lesions should be from as disparate regions of the body as possible when these areas are significantly involved. Target lymph nodes should not be selected from previously irradiated areas. If the sole measurable lesion lies within the field of prior radiotherapy, there must be evidence of disease progression in that lesion that has not been previously irradiated. If additional lesions are present but are not included in the target lesion assessment, they can be added as non-target lesions followed throughout the study. The cranial-caudal measurement of the spleen and longest diameter of the liver will be assessed at screening and all subsequent response evaluations.

Follow-up:

Radiologic tumor assessment will be performed according to SoA. Investigators will assess response and progression based on clinical/laboratory signs and symptoms. Radiology reports from a CT scan will be used to support the evaluation of complete and partial response.

Subjects who have signs and symptoms of disease progression outside of the scheduled study visits and assessments should be evaluated by the investigator with physical exam and blood counts with differential to determine if disease progression is present. The blood samples for response or disease progression determination should be confirmed by a central laboratory (samples from local laboratories can be used if central testing is unavailable). With Amendment 5.0, the blood samples for response or disease progression will be tested in local laboratories. Any suspected case of disease progression (in the absence of laboratory or

histopathologic changes meeting the criteria for PD) should be confirmed with a CT scan and should be reported to the sponsor or designee. Subjects may continue study treatment until progression is confirmed by a serial exam. In addition, when clinically appropriate, based on investigator-perceived risk-benefit assessment, a subject may continue treatment and remain under close observation until progression is confirmed. New anti-CLL therapy should be withheld if clinically appropriate in the absence of confirmed progressive disease.

If the subject's physical examination findings, laboratory evaluations (with hematology profile including absolute lymphocyte count, ANC, platelet count, and Hgb), and radiographic evaluations suggest that CR/CRi has been achieved in all response parameters, a bone marrow aspirate and biopsy must be obtained to confirm the CR and peripheral blood and bone marrow sample must be obtained to evaluate minimal residual disease (MRD). The bone marrow aspirate and biopsy must be done between 8-12 weeks of the CT imaging that supported the assessment of CR/CRi. Subjects who are otherwise in a complete remission but have bone marrow nodules that can be identified histologically, should be considered to have "nodular PR." Immunohistochemistry should be performed to define whether these nodules are composed of primarily T cells, lymphocytes other than CLL cells, or CLL cells. If the nodules are not composed of CLL cells, a CR can be documented provided all other criteria are met. In cases where cytopenic progression is suspected, a bone marrow aspirate or biopsy must be performed to distinguish autoimmune and drug-related cytopenias. In cases where Richter's transformation is suspected (e.g., rapidly progressive B-symptoms; bulky lymphadenopathy; organomegaly; anemia; a low platelet count; and elevated serum LDH, calcium, and β 2 microglobulin levels), diagnosis should be confirmed by biopsy of lymph nodes, bone marrow, or involved organs. Pathology analyses will be done for confirmation of Richter's transformation. Biopsy of the affected site is diagnostic and sufficient for confirmation. If an ancillary whole-body PET-CT scan (not required for study) is performed per local standard of care or at investigator discretion, the results of this scan should be captured in the eCRF as an unscheduled visit.

A central imaging service will be used to provide independent radiologic assessments for the purposes of the primary endpoint. All imaging assessments (including unscheduled visit scan) will be sent to the sponsor appointed central reader on an ongoing basis. Assessment of scans by BICR will be triggered only upon investigator-assessed progression for both arms and the BICR confirmation will be reported back to sites. If the BICR does not confirm disease progression, tumor assessments should be continued in line with the schedule of assessments. Since the primary analysis of the study is based on BICR, it is important that study treatment and scheduled imaging assessments continue until progression confirmed by BICR. After the final analysis and per Amendment 5.0, disease progression can be assessed by investigator.

If at the time of primary PFS analysis it is identified that a patient has disease progression by BICR that has not been identified by the investigator, the sponsor will contact the investigator to discuss whether continued treatment with study medication is appropriate.

The investigator must evaluate the response of the subject per IWCLL criteria (see Table 10).

Table 10 Response Assessment Criteria for CLL (modified from Hallek 2018) – IWCLL Criteria

Group	Parameter	CR a	PR b	PD	SD
A	Lymph nodes	None ≥ 1.5 cm	Decrease $\geq 50\%$ (from baseline) c	Increase $\geq 50\%$ from baseline or from response	Change of -49% to +49%
	Liver and/or spleen size d	Spleen size < 13 cm; liver size normal	Decrease $\geq 50\%$ (from baseline)	Increase $\geq 50\%$ from baseline or from response	Change of -49% to +49%
	Constitutional symptoms	None	Any	Any	Any
	Circulating lymphocyte count	Normal	Decrease $\geq 50\%$ from baseline	Increase $\geq 50\%$ over nadir with absolute count $\geq 5 \times 10^9/L$	Change of -49% to +49%
B	Platelet count	$\geq 100,000/\mu L$	$\geq 100,000/\mu L$ or increase $\geq 50\%$ over baseline	Decrease of $\geq 50\%$ from baseline secondary to CLL	Change of -49% to +49%
	Hemoglobin	≥ 11.0 g/dL (untransfused and without erythropoietin)	≥ 11 g/dL or increase $\geq 50\%$ over baseline	Decrease of ≥ 2 g/dL from baseline secondary to CLL	Increase < 11.0 g/dL or $< 50\%$ over baseline, or decrease > 2 g/dL
	Marrow	Normocellular, no CLL cells, no B-lymphoid nodules	Presence of CLL cells, or of B-lymphoid nodules, or not done	Increase of CLL cells by $\geq 50\%$ on successive biopsies	No change in marrow infiltrate

Abbreviations: CLL=chronic lymphocytic leukemia; CR=complete response; CT=computed tomography; PD=progressive disease; PR=partial response; SD=stable disease.

Note: CR, complete remission: all of the criteria have to be met; PR, partial response: for a PR at least 2 of the parameters of group A and 1 parameter of group B need to improve if previously abnormal. If only one parameter of both groups A and B is abnormal prior to therapy, only 1 needs to improve. PD, progressive disease: at least one of the above criteria of group A or group B has to be met; SD, stable disease: all of the above criteria have to be met. Constitutional symptoms alone do not define PD.

- a CRi (CR with incomplete bone marrow recovery) refers to subjects who fulfill all the criteria for a CR (including the bone marrow examinations), but have a persistent anemia, thrombocytopenia, or neutropenia apparently unrelated to CLL, but related to drug toxicity. Subjects who are otherwise in a complete remission, but bone marrow nodules can be identified histologically, should be considered to have “nodular PR.” Immunohistochemistry should be performed to define whether these nodules are composed of primarily T cells, lymphocytes other than CLL cells, or CLL cells. If the nodules are not composed of CLL cells, a CR can be documented provided all other criteria are met.

- b PRL (partial response with lymphocytosis): presence of lymphocytosis, plus $\geq 50\%$ reduction in lymphadenopathy and/or in spleen or liver enlargement, plus one of the PR criteria for platelets or hemoglobin have to be met.
- c Sum of the products of 6 or less lymph nodes (as evaluated by CT scans and physical examination in clinical trials, or by physical examination in general practice).
- d Spleen size is considered normal if <13 cm. There is not firmly established, international consensus of the size of a normal liver; therefore, liver size should be evaluated by imaging and manual palpation in clinical trials and be recorded according to the definition used in a study protocol.

For a detailed description of the response parameters see [Hallek 2018](#).

In particular, given the known mechanism of action of BCR-inhibiting agents including acalabrutinib, treatment-related lymphocytosis is an expected and frequent phenomenon observed with initiation (or re-initiation) of BTK inhibitors. An increase in blood lymphocyte count by itself does not uniformly indicate an increased tumor burden but may reflect redistribution of leukemia cells from lymphoid tissues to the blood. In such cases, increased lymphocytosis alone is not a sign of treatment failure or PD. The investigator may use their clinical judgment when assigning the overall response with blood lymphocyte count, as necessary.

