9.4 Outcome measures for analyses

9.4.1 Calculation or derivation of efficacy variables

9.4.1.1 Progression-free survival

PFS is defined as the time from the date of randomization until progression (assessed by the BICR per IWCLL 2018 criteria) or death from any cause, whichever occurs first. Subjects who withdraw from the study or are considered lost to follow-up without prior documentation of disease progression will be censored on the date of the last adequate disease assessment. Subjects who start new anticancer therapy before documentation of disease progression will be censored on the date of the last adequate disease assessment that is on or before the start date of the new anticancer therapy. For subjects without an adequate post-baseline disease assessment, PFS will be censored on the date of randomization unless they die within 2 visits of baseline.

PFS will also be obtained using the same derivation rule described above based on investigator assessment.

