**Table 3 Response Assessment Criteria for CLL (modified from [Hallek 2018](#)) – IWCLL Criteria**

Group	Parameter	CR a,b	PR c	PD	SD
A	Lymph nodes (target lesions only d )	None $\geq 1.5$ cm	Decrease $\geq 50\%$ (from baseline) e	Increase $\geq 50\%$ from baseline or from response	Change of -49% to +49%
	Liver and/or spleen size f	Spleen size <13 cm; liver size normal	Decrease $\geq 50\%$ (from baseline)	Increase $\geq 50\%$ from baseline or from response	Change of -49% to +49%
	Constitutional symptoms	None	Any	Any	Any
	Circulating lymphocyte count	Normal	Decrease $\geq 50\%$ from baseline	Increase $\geq 50\%$ over baseline	Change of -49% to +49%
B	Platelet count	$\geq 100,000/\mu\text{L}$	$\geq 100,000/\mu\text{L}$ or increase $\geq 50\%$ over baseline	Decrease of $\geq 50\%$ from baseline secondary to CLL	Change of -49% to +49%
	Hemoglobin	$\geq 11.0$ g/dL (untransfused and without erythropoietin)	$\geq 11$ g/dL or increase $\geq 50\%$ over baseline	Decrease of $\geq 2$ g/dL from baseline secondary to CLL	Increase < 11.0 g/dL or < 50% over baseline, or decrease > 2 g/dL
	Marrow	Normocellular, no CLL cells, no B-lymphoid nodules	Presence of CLL cells, or of B-lymphoid nodules, or not done	Increase of CLL cells by $\geq 50\%$ on successive biopsies	No change in marrow infiltrate

Abbreviations: CLL=chronic lymphocytic leukemia; CR=complete response; CT=computed tomography; PD=progressive disease; PR=partial response; SD=stable disease.

Note: CR, complete response: all of the criteria have to be met; PR, partial response: for a PR at least 1 of the parameters of group A and 1 parameter of group B need to improve if previously abnormal. If only one parameter of both groups A and B is abnormal prior to therapy, only 1 needs to improve. PD, progressive disease: at least one of the above criteria of group A or group B has to be met; SD, stable disease: all of the above criteria have to be met. Constitutional symptoms alone do not define PD.

- a CRi (CR with incomplete bone marrow recovery) refers to patients who fulfill all the criteria for a CR (including the bone marrow examinations), but have a persistent anemia, thrombocytopenia, or neutropenia apparently unrelated to CLL, but related to drug toxicity.
- b nPR (Nodular partial response): CR with the presence of B-lymphoid nodules in the bone marrow which reflect residual disease.

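### The hemoglobin row of the response table (Protocol Table 10, SAP Table 3) lets a CLL-related fall above 2 g/dL count as both stable disease and progression, and its stable-disease decrease limb omits smaller falls.

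*Protocol*

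**What the plan says.** Protocol Section 8.1.1, Table 10, gives the hemoglobin criterion for PD as "Decrease of ≥ 2 g/dL from baseline secondary to CLL". The SD cell of the same row closes with "or decrease > 2 g/dL".

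SAP Section 3.2.5, Table 3, repeats the row. Its SD cell reads "Increase < 11.0 g/dL or < 50% over baseline, or decrease > 2 g/dL", and its PD cell carries the same attribution to disease ("g/dL from baseline secondary to CLL").

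The notes under both tables give the same combination rule for these two categories. For PD, and then for SD, the protocol note says "at least one of the above criteria of group A or group B has to be met; SD, stable disease: all of the above criteria" must be met. One PD criterion is thus sufficient, while SD needs every SD criterion.

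The table bears on the primary endpoint in two ways. Protocol Section 9.4.1.1 defines PFS progression as "assessed by the BICR per IWCLL 2018 criteria". Protocol Section 8.1.1 tells the investigator to evaluate response with Table 10, and makes the central assessment of scans conditional on investigator-assessed progression. SAP Section 3.2 adds that responses are taken as judged and are not programmed.

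**The concern.** Two response categories that are meant to exclude each other share part of their range. The threshold that separates stable disease from progression on hemoglobin points the wrong way in the SD cell: as printed, the larger fall is stable and the smaller fall is not mentioned.

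At stake is whether a hemoglobin-based progression is recorded as a progression. Section 8.1.1 asks for CT confirmation of suspected progression only where no laboratory or histopathologic change already meets the PD criteria, so a laboratory change alone can establish PD. An investigator who follows the SD cell could leave such a patient as SD, and the central read would not be triggered at that visit. The trial is open-label, so an unclear boundary leaves room for judgment that differs between sites. The table still matters after the final analysis: under Amendment 5.0, investigator-assessed progression can qualify an Arm B patient for crossover (Protocol Section 6.8).

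**Working it through.** No sample size, power or alpha figure is involved. The check is logical: apply the two printed cells to a set of hemoglobin falls and see which categories result.

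Inputs, identical in Protocol Table 10 and SAP Table 3:

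- PD cell: fall ≥ 2 g/dL and secondary to CLL.
- SD cell, decrease limb: fall > 2 g/dL, with no attribution condition.
- Combination rule: one PD criterion gives PD; SD needs all SD criteria.

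| Fall from baseline (g/dL) | Secondary to CLL? | PD cell met | SD decrease limb met | Result |
|---|---|---|---|---|
| 0.5, 1.0, 1.9 | yes or no | no | no | neither |
| 2.0 | yes | yes | no | PD only |
| 2.0 | no | no | no | neither |
| 2.1, 3.0, 4.0 | yes | yes | yes | both |
| 2.1, 3.0, 4.0 | no | no | yes | SD only |

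**Overlap.** Every tested CLL-related fall above 2 g/dL meets both cells. If all other parameters are in their SD range, the SD rule (all criteria) and the PD rule (any criterion) are satisfied together.

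**Gap.** Falls below 2 g/dL meet neither the PD cell nor the SD decrease limb. They reach SD only if a fall is read as an increase of less than 50%. That reading does not help, because every fall, however large, is then an increase of less than 50%, and the overlap with PD remains.

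**Precedence.** Neither table note says that PD overrides SD. The only ordering in the SAP is the best-overall-response ranking in Section 3.3.3. That ranking chooses among responses already assigned and does not settle which category a single visit receives.

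**Comparison row.** For platelets, PD is a decrease of at least 50% and SD is a change of -49% to +49%. On whole percentages from -60 to +60, no value meets both, so the platelet row does not share the fault.

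**Transcription.** The hemoglobin wording is the same in two separate documents. The tables differ elsewhere: in the lymphocyte PD cell, and in the number of group A parameters needed for PR (2 in the protocol, 1 in the SAP). A PDF-reading error is therefore unlikely.

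**Would reversing the sign be enough?** As an illustration only, with the SD limb read as fall < 2 g/dL, no tested fall meets both cells and falls below 2 g/dL become SD. But falls of 2.0, 2.1, 3.0 and 4.0 g/dL not secondary to CLL then meet neither cell. One changed character would replace an overlap with a different gap.

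**The case against.** The strongest reply is that this is a sign slip with little practical effect. One PD criterion is enough, so an investigator who attributes a 3 g/dL fall to CLL has already met PD whatever the SD cell says. Where cytopenic progression is suspected, Protocol Section 8.1.1 and SAP Section 3.2.4 require a marrow examination. Both tables send the reader to the cited guideline for detail. Because responses are judged and not programmed, no algorithm executes the wrong sign. The row is the same for both arms, and nothing in the documents points to a direction of bias.

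Most of this stands, and it is why the number of affected patients is probably small. It does not remove the contradiction. The marrow requirement applies only once progression is suspected, and no text tells a reader which of two satisfied categories to record.

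Three stronger readings are tempting, and the documents do not support them:

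- A reader might infer that every hemoglobin fall above 2 g/dL is affected. The PD cell requires the fall to be secondary to CLL; a drug-related or autoimmune fall above 2 g/dL meets SD only and creates no conflict.
- A reader might infer that BICR reads this table. Protocol Section 8.1.1 and SAP Section 3.2.5 assign it to the investigator, the protocol describes the central assessment as radiologic, and the BICR charter is not among the documents.
- A reader might infer that a missed trigger loses the event. All imaging goes to the central reader on an ongoing basis, and the protocol foresees BICR progression that the investigator had not identified. Whether this would catch a progression shown by hemoglobin alone cannot be told from the documents.

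**Conclusion.** The hemoglobin row is wrong as written in both documents. The SD and PD cells overlap for CLL-related falls above 2 g/dL, and the SD decrease limb does not cover falls below 2 g/dL. This is more than a slip in background text, because the investigator must use the table and the investigator's progression call triggers the central read.

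The effect on PFS cannot be sized. The documents do not say how often hemoglobin fell by 2 g/dL or more, or whether any visit was classified on the SD cell. One reclassified patient would be 1/48 = 2.1% of the 48 BICR events at the 03 January 2024 cutoff (Protocol Section 1.2). A reader might take that as an estimate of impact; it is only the weight of a single event, and there is no evidence that any event was missed or misdated. Nothing here shows that the trial's conclusion would change.

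The verdict rests on the printed wording and on there being no precedence rule elsewhere. A site manual or the BICR charter, neither of which is available, could contain one.

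**What to change.** In Protocol Table 10 and SAP Table 3, reconcile the SD and PD hemoglobin cells so that three conditions hold:

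1. The cells do not overlap.
2. Falls below 2 g/dL are covered.
3. Falls of 2 g/dL or more that are not secondary to CLL have a stated category.

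The sponsor should settle the wording against the cited guideline; reversing the inequality alone does not meet the third condition.

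Editing the tables cannot change assessments already made, and the 03 January 2024 cutoff was treated as the final analysis. The sponsor should therefore also query two groups: assessments recorded as SD despite a hemoglobin fall of at least 2 g/dL from baseline, where an event could be hidden, and reads where hemoglobin was the only PD criterion. The CSR should report whether any PFS event or date changes.

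The cost is a short text correction in two tables, one data query with review of the visits it finds, and a statement in the CSR.
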